Study Protocol

Study Title:

To investigate the potential effectiveness of mirror-aided cross-education using the innovative 'Mirror Strengthening Device' compared to mirror therapy alone in post-stroke upper limb recovery: A pilot randomised feasibility study.

Document creation date: February 4th 2022

NCT number [not yet assigned].

Identifiers: [NCT ID not yet assigned]

Study Protocol

To investigate the potential effectiveness of mirror-aided cross-education using the innovative 'Mirror Strengthening Device' compared to mirror therapy alone in post-stroke upper limb recovery: A pilot randomised feasibility study.

Study Objectives:

1. To conduct a randomised controlled pilot feasibility study to examine the effects of mirror-aided cross-education using a specially designed Mirror Strengthening Device in post stroke upper limb recovery.
2. To examine the feasibility of mirror-aided cross-education using a specially designed Mirror Strengthening Device in this patient cohort
3. To investigate any adverse effects of mirror-aided cross-education using a specially designed Mirror Strengthening Device in this population.

Study Design:

The Design is an assessor blinded, randomised control pilot feasibility trial. The independent assessor, who is blinded to the treatment assignment, will perform all the assessments. After baseline measurements are obtained, the patients will be randomly assigned to the intervention or control group using computer generated block random numbers where gender and function will be considered. A statistician who will be blinded to the research protocol and not otherwise involved in the trial will conduct the random number programme.

Setting:

Assessments: Exercise Physiology Lab, IT Sligo.

Intervention: Participants own home.

Intervention:

Both groups will perform a 5 minute warm up, 5 minute cool down and main set of exercises consisting of up to 4 sets of 5 repetitions of 5 dynamic shoulder exercises.

They will be instructed to perform the concentric and eccentric phases of the contraction at 3 seconds and 4 seconds, respectively, rest for 2 sec between contraction and rest between sets. The full set should take approximately 30mins.

Participants will be asked to complete the intervention 5 days a week for 4 weeks.

Experimental Group:

The experimental group will be performing the repetitions with a set resistance on the Mirror Strengthening Device

Control Group:

The control group will be performing the repetitions with no resistance on the Mirror Strengthening Device.

Positioning:

Participants will be seated in a chair in front of their own kitchen table. The elbow is flexed at 90 degrees and kept in close to the trunk not resting on anything. Palm of hand is facing the exercise device and holding a pulley. The untrained limb will be positioned in a similar position to the training limb supported on the table behind the exercise device with the shoulder slightly flexed forward to allow this positioning.

Participants will view the mirror reflection of their less- affected limb in the mirror which is positioned lateral to the mid-sagittal plane of the more - affected limb before any strength training commences.

The participant will be asked to look at the reflected image of their less-affected limb in the mirror as they train. They will then complete the prescribed HEP.

Rests:

Participants will be informed that breaks can be taken during the training session for reasons of tiredness or fatigue if required.

Training Diary:

All participants will be provided with a training diary. They will be asked to completed this before and after each training session.

Adverse Effects:

All participants will be asked to record any changes before and after each training session in the HEP record book and to contact Principal Researcher with any adverse effects.

Outcome Assessments:

Outcome Measures will be taken before and after the 4-week home exercise programme and at 3 months follow up and will include:

Primary:

Isokinetic Strength: (Biodex System 4 Pro with advantage software)

Grip Strength: (Hand held dynamometer)

Secondary:

Fugl-Meyer Upper Extremities Test

Stroke Impact Scale

Modified Ashworth Scale (MAS) for spasticity).

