## Statistical Analysis

We will analyse the data using Excel and SPSS for Windows. Paired T tests will be used to compare before and after data in both groups.

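### The trial randomises to two arms with gender and function considered, but the only stated analysis neither compares the arms nor uses those factors

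*Protocol*

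**What the plan says.** The Study Title in the protocol is comparative: the device is to be "compared to mirror therapy alone in post-stroke upper limb recovery: A pilot randomised feasibility study". Under Study Design, "After baseline measurements are obtained, the patients will be randomly assigned to the intervention or control group", and the allocation is made "using computer generated block random numbers where gender and function will be considered". The protocol does not say whether this means stratification, how function is measured or cut, or what the block size is.

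Under Outcome Assessments, the primary outcomes are grip strength and "Isokinetic Strength: (Biodex System 4 Pro with advantage software"), both continuous. On timing: "Outcome Measures will be taken before and after the 4-week home exercise programme and at 3 months follow up".

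The SAP, Statistical Analysis, names the software and then one method: "Paired T tests will be used to compare before and after data in both groups". It mentions no arm difference, between-arm test, confidence interval, covariate or stratum. The SAP text available for review is not the whole file, so this point rests on the part that could be read.

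**The concern.** Randomisation exists so that two arms can be compared, and the design goes further by taking gender and function into account. The analysis then uses neither feature. A paired test in each arm asks whether that arm changed. Both arms do the same exercises and differ in resistance, so each arm's change includes whatever the arms share: practice with the tests, natural recovery and the unresisted exercise itself. A significant change in one arm and not in the other does not estimate the effect of resistance.

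There is a second, smaller matter. Gender and function may well predict strength. If arms are balanced on predictive factors and then compared without them, the reported standard error still includes variation that the design has removed. The interval is then too wide and the test conservative. In a small pilot, a real difference becomes easier to miss and the result is less useful for planning.

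**Working it through.** **No figure to reproduce.** The documents give no sample size, alpha, standard deviation or standard error. Assumed below: two-sided 5%, 1:1 allocation, four strata (gender × function) balanced exactly, total N of 16 or 32, and a share R² of outcome variance explained by the two factors of 0.1 to 0.4.

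**Step 1: What the stated analysis estimates.** A paired test in one arm estimates the mean of (after − before) in that arm. The comparative question needs the difference between two such means, or between adjusted post-treatment means. The SAP text contains neither, so there is no arm-comparison interval to be right or wrong.

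**Step 2: Unadjusted comparison of post-treatment values.** With total variance 1, the true variance of the arm difference under exact balance is (1−R²)·4/N. The variance reported without the factors averages [(1−R²) + R²·N/(N−2)]·4/N. The CI width ratio, without to with the factors, is therefore about

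sqrt{[(1−R²) + R²·N/(N−2)]/(1−R²)} × t(N−2)/t(N−4).

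- N=16, R²=0.1: sqrt(1.0143/0.9) × 2.145/2.179 = 1.062 × 0.984 = 1.05.
- N=16, R²=0.4: sqrt(1.0571/0.6) × 0.984 = 1.327 × 0.984 = 1.31.
- N=32, R²=0.4: sqrt(1.0267/0.6) × 2.042/2.048 = 1.308 × 0.997 = 1.30.

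Simulated null trials agree: ratios of 1.04 to 1.32. Type I error without the factors is about 1–4%, and about 5% with them.

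**Step 3: Is the precision lost?** At N=40 and R²=0.3 (20,000 simulated trials), the true standard error was 0.266 both with and without the factors. The reported standard error was 0.319 without them and 0.265 with them. The estimate keeps the benefit of balance. Only the reported error fails to show it.

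**Step 4: With baseline in the model.** Assume an overall baseline–follow-up correlation ρ of 0.7 to 0.9 and factors that shift both measurements equally. Residual variance is 1−ρ² with baseline alone, and (1−R²)·{1 − [(ρ−R²)/(1−R²)]²} with baseline and the factors.

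- Baseline alone multiplies the standard error by sqrt(1−ρ²): sqrt(0.51) = 0.71 at ρ=0.7 and sqrt(0.19) = 0.44 at ρ=0.9. This is the large gain.
- Adding the factors, largest effect (ρ=0.7, R²=0.4, N=32): sqrt(0.51/0.45) × 2.045/2.052 = 1.065 × 0.997 = 1.06.
- Adding the factors, smallest effect (ρ=0.9, R²=0.1, N=16): sqrt(0.1900/0.1889) × 2.160/2.201 = 1.003 × 0.982 = 0.98.

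Simulation (4,000 trials per setting) gave ratios of 0.98–1.06, with type I error without the factors of 4.1–5.4%. For change scores the ratio was 0.99–1.00, because stable gender and function differences cancel.

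**The case against.** The strongest objection is that the harm from omitting the factors falls on an analysis nobody has planned. A reader might infer that the trial's arm-comparison intervals will be 5–31% too wide, or that the precision gained by balancing is thrown away. The documents support neither. No arm comparison is stated, and Step 3 shows that the estimate keeps its precision. The 5–31% also applies only to post-treatment values compared without baseline. A comparison of change scores, the nearest extension of a before–after plan, would lose almost nothing. This objection stands, and it places the main defect in the missing comparison.

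Secondly, the protocol says only that the factors are considered, which does not establish stratification. That also stands. If allocation is not stratified, type I error is about 5% with or without adjustment. Adjusting post-treatment values would then still usually narrow the interval: for R² of 0.2 or more, unadjusted intervals were 1.02–1.20 times as wide at N=16 and 1.02–1.25 at N=32. At N=16 with R²=0.1, adjustment cost about 4%.

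Thirdly, a reader might take function to mean the "Fugl-Meyer Upper Extremities Test" and ask for it to drive the allocation. The protocol lists that test only as a secondary outcome and does not link it to randomisation. Adopting it would change the allocation design, and the fix does not need it.

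Finally, a pilot feasibility study need not test efficacy. That is fair, but the title and first objective are about effects, and an adjusted difference with its interval can be reported without resting a conclusion on a p-value.

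**Conclusion.** The point holds in this form: the design is comparative and takes gender and function into account, while the analysis supplied compares no arms and uses neither factor. The missing between-arm estimate is the consequential part, and baseline adjustment gives most of the statistical gain.

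Omitting gender and function is a matter of efficiency. It makes inference conservative, and it neither biases the estimate nor inflates false positives. Its size is about 5–31% in CI width for unadjusted post-treatment values, and about -2% to +6% once baseline is in the model. These ranges rest on an assumed N of 16–32, R² of 0.1–0.4 and, for the first range, truly stratified allocation. The second range also needs ρ of 0.7–0.9 and factors acting equally at both times. If gender or function also predicts change, more gain would remain, but the documents give no basis for putting a figure on it.

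**What to change.** In the SAP, make the main analysis a between-arm ANCOVA for each strength outcome. The model terms are arm, the baseline value of that outcome, gender, and function as defined for the randomisation. Report the adjusted arm difference with a 95% CI, and say which post-baseline assessment it refers to. The paired tests can stay as descriptive summaries of change within each arm.

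In the protocol, state how gender and function enter the allocation and how function is defined, so that the list and the model use the same variable.

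The baseline data are collected before randomisation and SPSS fits the model, so the change is a few sentences. If each factor enters as a single term, gender and function cost two degrees of freedom. At N=16 that raises the t multiplier from 2.160 to 2.201 (about 2%), so the interval may widen slightly in a very small sample.

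### The home-training records are prompted only by sessions that take place, so a wholly blank session cannot be classed as not done or as done but not recorded

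*Protocol*

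**What the plan says.** The second item under Study Objectives in the Protocol is "To examine the feasibility of mirror-aided cross-education using a specially designed Mirror Strengthening Device in this patient cohort". Adherence is not named there, and no feasibility measure is defined.

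Under Setting, the place of training is given as "Intervention: Participants own home". Under Intervention, the schedule is "Participants will be asked to complete the intervention 5 days a week for 4 weeks".

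Two records of the home programme are mentioned:

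- Training Diary: "All participants will be provided with a training diary", followed by "They will be asked to completed this before and after each training session".
- Adverse Effects: participants are to "record any changes before and after each training session in the HEP record book", and to contact the researcher about adverse effects. The Protocol does not say whether this book is the diary under another name or a second document.

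No supervised session, home visit, telephone call, device log or diary check is described. The SAP's Statistical Analysis section reads "Paired T tests will be used to compare before and after data in both groups". It gives no summary of sessions done. Part of the SAP was not available for review, so nothing below rests on its silence.

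**The concern.** Both records are prompted by a training session. A participant who follows the instruction to the letter writes nothing on a day without training. A participant who trains and forgets the diary also leaves nothing. The two cases look the same on paper, and the stated instruction does not ask why a session did not happen.

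This matters because the programme is unsupervised and the arms differ only in whether resistance is applied. Sessions completed is a natural measure for objective 2. The reasons for missed sessions (load, tiredness, set-up or device trouble, lack of time) would show what to change before a larger trial. It also bears on objective 1: if strength does not improve, the reader will want to know whether the training was done. None of this can be reconstructed reliably once the 4 weeks are over.

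**Working it through.** The documents give no adherence target, recording rate or sample size, so there is no figure of the plan's own to reproduce. The check is whether the diary count can identify adherence.

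**Inputs from the Protocol.** Planned sessions per participant: 5 × 4 = 20. Entries requested: 2 per session, so 2 × 20 = 40.

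**Model.** Let a be the share of planned sessions done and c the share of done sessions that are written up. Expected recorded sessions are

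D = 20 × a × c.

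One observed D cannot separate a from c. With D = 14 (an assumed count, for illustration):

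- a = 70%, c = 100%: 20 × 0.70 × 1.00 = 14
- a = 80%, c = 87.5%: 20 × 0.80 × 0.875 = 14
- a = 90%, c = 77.8%: 20 × 0.90 × 0.778 = 14
- a = 100%, c = 70%: 20 × 1.00 × 0.70 = 14

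**Bounds that need no recording rate.** If no entry is false, true adherence lies between D/20 and 100%:

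- 10 recorded: 50% to 100%
- 14 recorded: 70% to 100%
- 18 recorded: 90% to 100%

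The number of blanks, 20 − D, is known. Its split into sessions not done and sessions not recorded is not.

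**Illustration with assumed recording rates.** Take c between 70% and 95%.

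- True adherence 80%: 0.80 × 0.70 = 56%; 0.80 × 0.95 = 76%
- True adherence 90%: 0.90 × 0.70 = 63%; 0.90 × 0.95 = 85.5%

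The shortfall runs from 80 − 76 = 4 to 90 − 63 = 27 percentage points. That range follows wholly from the chosen inputs.

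**Comparison between arms, also with assumed rates.**

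- Equal recording of 85% in both arms: true 80% v 60% appears as 0.80 × 0.85 = 68% v 0.60 × 0.85 = 51%. The ratio is unchanged (60/80 = 51/68 = 0.75).
- Unequal recording, 95% v 70%: two arms that both did 80% appear as 76% v 56%, a spurious gap of 20 points.
- Unequal recording the other way: true 80% recorded at 70% gives 56%, and true 60% recorded at 93.3% gives 0.60 × 0.933 = 56%. A real gap of 20 points disappears.

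**The case against.** Several objections have force.

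- **The form is not shown.** The Protocol says when the diary is completed, not what it contains. A dated line for each day or a comments box cannot be excluded. A reader might infer that reasons for missed sessions are not collected at all; the documents do not go that far. What stands is that the stated instruction would not prompt anyone to fill in such a line on a day without training.
- **There may be a second record.** A reader might take the diary to be the only record of home training. The HEP record book is also mentioned, and if it is a separate document, a session missing from one may appear in the other. Likewise, a before entry without an after entry reveals a half-recorded session. Neither helps with a session blank throughout, since both records have the same trigger.
- **A difference between arms can still show.** A reader might infer that the trial could not detect more skipped sessions in the resistance arm. That is too strong. Both arms have the same diary and rule, and with similar recording rates the ratio between arms is preserved. The plan gives no reason to expect recording to differ, but it also offers no way to check.
- **Adherence is the reviewer's choice of measure.** Objective 2 does not name it, and the wider gap is that no feasibility measure is defined. Sessions completed out of 20 is nonetheless a natural candidate for an unsupervised home programme.
- **Even the direction of error is uncertain.** Forgotten entries push the count down, but back-filled or false entries push it up. The bounds hold only if there are none.

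**Conclusion.** The concern holds in a limited form. On the stated instruction, a wholly blank session cannot be assigned to not done or to done but not recorded. The diary count therefore bounds a participant's true adherence only between D/20 and 100%, assuming no false entries; 14 recorded sessions fit 70% to 100%. What is lost is the absolute level of adherence, the reasons for missed sessions, and protection against recording that differs by arm. This limits what the trial can say on objective 2.

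A reader might be tempted to quote the 4 to 27 point shortfall as the expected error. It is an illustration from assumed recording rates of 70% to 95% and assumed adherence of 80% and 90%; the documents support none of these figures.

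The strength outcomes do not come from the diary, so they are not distorted directly. This is a cheap improvement worth making before the diary is printed, not a flaw that invalidates the design.

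**What to change.** Replace the per-session completion rule with a diary that has one pre-numbered line for each of the 20 planned sessions.

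- Each line is ticked as done, part done or not done. For part done, the number of sets completed is entered, because the Protocol sets a maximum of four sets and not a fixed number; what counts as done should be defined with that in mind.
- If part done or not done, one reason is ticked: discomfort, tiredness, resistance too hard, device or set-up problem, no time, or other.
- A carer may tick on the participant's behalf.
- State whether the HEP record book is the same document.
- Report sessions done out of 20 for everyone randomised, by arm, with blank lines as a separate category and reasons tabulated by arm.

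The cost is reformatting one page before printing and adding one table, with no extra visits or staff. The downside is that participants are asked to tick a line on days they do not train. The record remains unverified self-report and some lines will still be left blank, so the ambiguity is reduced and made visible, not removed.

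### Prompted adverse-effect recording ends with the last training session in week 4; after that only spontaneous contact is described, so delayed or persisting effects may be missed while benefit is measured to 3 months.

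*Protocol*

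**What the plan says.** Adverse effects are one of the three study objectives. Objective 3 reads: "To investigate any adverse effects of mirror-aided cross-education using a specially designed Mirror Strengthening Device in this population".

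The protocol's Adverse Effects section gives two routes for collecting them:

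- **Prompted record.** "All participants will be asked to record any changes before and after each training session in the HEP record book". The Training Diary section sets the same timing: "They will be asked to completed this before and after each training session".
- **Spontaneous contact.** The Adverse Effects sentence continues "and to contact Principal Researcher with any adverse effects". No end date is given, and the route is not limited to training days.

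The Intervention section fixes how long sessions last: "Participants will be asked to complete the intervention 5 days a week for 4 weeks".

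The Outcome Assessments section fixes how long participants are followed: "Outcome Measures will be taken before and after the 4-week home exercise programme and at 3 months follow up". The measures listed there are isokinetic strength, grip strength, the Fugl-Meyer upper-extremity test, the Stroke Impact Scale and the Modified Ashworth Scale. No adverse-effect enquiry is described at any of the three assessments.

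**The concern.** The two sides of the benefit-harm picture are gathered differently after week 4. Benefit is measured at a scheduled visit for every participant, up to 3 months. Harm, once the sessions end, is recorded only if a participant decides to get in touch.

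During the programme the record works well for delayed effects, because the entry made before the next session can pick up whatever developed since the last one. After the final session there is no next entry. The same holds for a participant who stops training early: with no further session, nothing prompts an entry.

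What is at stake is how a negative finding can be read. If the trial reports no adverse effects after week 4, the reader cannot tell whether there were none or whether nobody was asked. For a feasibility trial of a new device used at home, that is a gap in one of its three stated objectives.

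**Working it through.** The documents give no sample size, adverse-effect rate or reporting rate, so there is no figure of the plan's own to reproduce. The check is of coverage over time.

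**Inputs**

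- Sessions: 5 days a week for 4 weeks (Protocol, Intervention).
- Entries: one before and one after each session (Protocol, Training Diary and Adverse Effects).
- Follow-up: a visit at 3 months, with the starting point of the 3 months not stated (Protocol, Outcome Assessments). Three months is taken as 91 days.

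**Prompted record during training**

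- Sessions = 5 × 4 = 20.
- Entries = 20 × 2 = up to 40.
- Programme length = 4 × 7 = 28 days. All 28 are counted as covered, since entries before each session can also reflect the days in between.

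**Calendar time without a prompted record**

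Share = (total days − 28) / total days.

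| Reading of 3 months | Total days | Days without prompt | Share |
|---|---|---|---|
| From baseline | 91 | 91 − 28 = 63 | 63/91 = 0.692, about 69% |
| From programme end | 28 + 91 = 119 | 119 − 28 = 91 | 91/119 = 0.7647, about 76% |

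On either reading most of the participant's time in the trial, and all of it after training, has no prompted record.

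**Can this be turned into a number of missed events?** Not from the documents. Let s be the share of adverse effects that arise after training and q the share of those reported by spontaneous contact, with prompted capture taken as complete. The share missed is then s × (1 − q). Both s and q have to be assumed:

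- s = 5%, q = 50%: 0.05 × 0.5 = 2.5%.
- s = 10%, q = 50%: 0.10 × 0.5 = 5%.
- s = 50%, q = 0: 0.50 × 1 = 50%.
- any s, q = 100%: 0%.

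With s from 5% to 50% and q from 0 to 100%, the result runs from 0% to 50%. The spread comes entirely from the assumptions, so it shows only that the size is unknown.

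**The case against.** The strongest reply is that prompted recording sits where the exposure is. All 20 planned sessions are covered, with up to 40 entries, and no device use is scheduled afterwards. A day after training need not carry the same risk as a training day. This stands: the 69% to 76% is a share of calendar time and must not be read as a share of events lost. It does not close the gap, because effects that persist or appear after the last session are still effects of the training.

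Second, the contact instruction is open-ended and applies to everyone. That also stands, and it is why the point concerns prompted collection only. A spontaneous route depends on the participant choosing to use it.

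Third, the list of measures is introduced by "Outcome Measures will be taken before and after the 4-week home exercise programme and at 3 months follow up and will include" and is not presented as a full visit schedule, so an enquiry might be made without being written down. The accurate statement is therefore that none is described. The Modified Ashworth Scale and Stroke Impact Scale at 3 months could show some worsening, but they are outcome scores and do not serve as adverse-effect collection.

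Two stronger readings are tempting, and the documents do not support them.

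- **A reader might infer that adverse effects will be under-counted.** Without an event rate or a reporting rate this cannot be shown. The most that follows is that later effects may be missed.
- **A reader might infer that uncollected reactions to the strength tests also bias objective 3.** Objective 3 concerns effects of training with the device, so a reaction to the test listed as "Isokinetic Strength: (Biodex System 4 Pro with advantage software" is outside it. Baseline testing comes before randomisation and training, so the entry before session 1 can pick up a lasting reaction to that test before any device exposure. Both arms have the same assessments, so comparing arms also guards against blaming resistance training for a test reaction.

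**Conclusion.** The point holds in a limited form. Prompted adverse-effect recording is linked to training sessions and ends with the last one. From then on, including at the post-programme and 3-month visits, spontaneous contact with the Principal Researcher is the only route described. About 69% to 76% of calendar time has no prompted record, depending on where the 3 months start, with 3 months taken as 91 days and all 28 programme days counted as covered.

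Delayed or persisting effects may be missed, by an amount the documents do not allow anyone to estimate. The consequence for objective 3 is that absence of late adverse effects could not be distinguished from absence of enquiry. Part of the SAP is not available for review, so nothing is concluded here about how adverse effects would be analysed. The conclusion rests on the data collection described in the protocol.

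**What to change.** At the post-programme and 3-month visits, have every participant in both arms self-complete the same brief adverse-effect question: any new or worsened problem since the last entry or visit, when it began, and whether it has resolved. Return the form to the Principal Researcher, so that the independent assessor does not see it and stays blinded as Study Design requires. Ask it also of participants who stopped training early.

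State in the protocol that adverse effects for objective 3 are reported by arm from baseline to the 3-month visit, separately for weeks 0-4 and after week 4. The split matters because the two periods are collected differently: session by session in the first, by recall at visits in the second. State also whether the 3 months run from baseline or from programme end.

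The cost is a short form at two visits that already take place, plus a few lines of protocol text. The downside is imperfect recall over the weeks after the programme and more minor events reported. Both are modest, and asking both arms the same question keeps the comparison fair.

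### The post-treatment visit is timed by the home programme with no window or rule for early stoppers, and the paired t-test drops anyone without a post-programme value, so results may be limited to those who return

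*Protocol*

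**What the plan says.** Timing of assessments is given in one sentence of the Protocol, under Outcome Assessments: "Outcome Measures will be taken before and after the 4-week home exercise programme and at 3 months follow up". The training period is set under Intervention: "Participants will be asked to complete the intervention 5 days a week for 4 weeks". Training takes place at home, while the Setting section sends participants elsewhere to be measured: "Assessments: Exercise Physiology Lab, IT Sligo". Under Study Design, baseline comes before allocation: "After baseline measurements are obtained, the patients will be randomly assigned to the intervention or control group".

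The supplied SAP text on analysis is two sentences, one on software and one on method: "Paired T tests will be used to compare before and after data in both groups". It does not mention the 3-month data, an analysis population or missing values. Part of the SAP was not available for this review, so those statements apply to the supplied text only.

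**The concern.** Two gaps act together. First, the post-treatment visit is tied to a programme that each participant carries out at home, and a participant may stop it or let it slip. Staff are not told when to measure someone who stops in week 2, or whether to measure them at all. Nor are they told whether someone who pauses is measured on the calendar date or when the sessions are finished. Second, the stated test can use only participants with both values, so each missed post-programme visit removes a randomised participant from the result.

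One arm trains against resistance and the other does not, so it is plausible that stopping, and with it attendance, differs between arms. If those who fail to return would have changed by a different amount, each arm's mean change is distorted, and so is any comparison of the arms. Adding a between-arm test would not cure this, because it would run on the same reduced set of people. Separately, values taken at different times since randomisation mix the effect of training with elapsed time.

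Feasibility is a stated objective, so who returns, and from which arm, is itself a result the study should produce.

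**Working it through.** The supplied text gives no sample size, SD, effect size or dropout rate, so the plan has no figure to reproduce. The check has two parts.

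**1. The texts side by side**

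- *Which value can be lost.* Randomisation follows baseline, so every randomised participant should have a baseline value. Loss falls on later values, after allocation.
- *How it can be lost.* Training is at home and measurement is in a laboratory, so the post-programme value needs a separate visit. Someone who trained fully can miss it, and someone who stopped can still attend.
- *When the visit falls.* The programme's end can be read as a calendar point (week 4) or as completion of the prescribed sessions (5 × 4 = 20). The readings agree for a participant who keeps to schedule. For one who stops in week 2, the first gives a visit at about week 4 and the second gives no defined visit. For one who pauses, the second gives a late visit.
- *Where the 3 months start.* Counting from baseline and counting from programme end give dates about 4 weeks apart, as long as the whole intervention.
- *What the test uses.* A paired t-test works on within-person differences. Without a post-programme value there is no difference to compute, and a 3-month value cannot stand in for it.

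**2. How large the effect could be**

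Let *d* be the share of an arm with no post-programme value, *m_o* the mean change in those observed, *m_m* the mean change those missing would have had, and *g = m_o − m_m*, in SD of change. Then

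error in the arm's mean change = *m_o* − [(1 − *d*)*m_o* + *d* *m_m*] = *d* × *g*.

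Both *d* and *g* are assumptions. Over a range:

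| Share missing | g = 0 | g = 0.5 SD | g = 1.0 SD |
|---|---|---|---|
| 0% | 0 | 0 | 0 |
| 10% | 0 | 0.05 | 0.10 |
| 20% | 0 | 0.10 | 0.20 |
| 30% | 0 | 0.15 | 0.30 |

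A simulation of one million changes with *d* = 0.20 and *g* = 0.5 gave 0.099, against 0.20 × 0.5 = 0.10 from the formula. If those missing would have done better, the sign turns: 0.20 × (−0.5) = −0.10 SD.

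For a comparison of experimental (E) with control (C), the error is *d_E g_E − d_C g_C*. With a common gap of 0.5 SD:

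- 10% missing in each arm: (0.10 − 0.10) × 0.5 = 0
- 20% E, 10% C: 0.10 × 0.5 = 0.05 SD
- 30% E, 10% C: 0.20 × 0.5 = 0.10 SD
- 10% E, 30% C: −0.20 × 0.5 = −0.10 SD

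The supplied SAP plans no between-arm test, so this last set applies to a comparison that a reader would make, or that the fix below would add. It does not apply to the stated within-group tests.

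**The case against.** The strongest reply is that the programme is named by its length. An ordinary reader could take the sentence to mean a visit at about week 4 for everyone, including those who trained little or stopped. Nothing in the documents says that such people go unmeasured. This stands, and it rules out a tempting stronger reading, namely that the trial's result describes programme completers and not all who were randomised. Stopping the exercises is not the same as missing the visit. The paired test selects those with a post-programme measurement, and if everyone attends, it covers everyone.

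A reader might also infer that the missing data will flatter the experimental arm. That is not supported either. The documents say nothing about who stops or why; controls training without resistance might stop more often, or good responders might leave. Direction and size are both open.

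A population or follow-up rule may sit in the part of the SAP that could not be seen. And in a pilot feasibility study, precise estimation of effect is not the only aim, which limits the weight of the point.

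What survives is that two reasonable readings of the visit at which the primary outcomes are measured exist, the supplied text does not choose between them, and the stated test has no means of using a participant who lacks that visit.

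**Conclusion.** The point holds in conditional form. The supplied text leaves the timing of the post-treatment visit, the origin of the 3-month visit and the assessment of early stoppers unstated. The stated test excludes any randomised participant without a post-programme value and makes no use of the 3-month value. The result may therefore be limited to those who return.

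The resulting error is zero if nobody is missing or if those missing would have changed by the same amount. In the illustrations above it reaches 0.30 SD within an arm, at 30% missing and a 1.0 SD gap. These figures rest wholly on assumed inputs and are not a forecast. The change is worth making before data collection because it is cheap and is right under either reading of the visit. It does not show that the trial is invalid.

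**What to change.** **Protocol, Outcome Assessments.** Set the post-treatment visit at a fixed time from randomisation, long enough to allow for the 4 weeks of training, with a window (for example one week either side). Time the 3-month visit from the same date. Randomisation is a better anchor than programme start, because a participant who never starts would otherwise have no visit date. State that every randomised participant is invited to both visits whatever their adherence, unless they withdraw consent to assessment. This is the essential step, since no analysis can recover outcomes that were never collected.

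**SAP, Statistical Analysis.**

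- For the continuous outcomes, replace the within-group paired t-tests with a comparison of the arms as randomised. Use a repeated-measures model adjusted for baseline that includes both follow-up visits, so that a participant who misses one visit still contributes the other.
- Analyse the Modified Ashworth Scale, which is ordinal, with an ordinal or rank method.
- Report the number missing at each visit by arm as a feasibility result.
- State the limits: the model assumes that data are missing at random, which fails if attendance depends on unobserved response, and participants who miss both follow-up visits contribute no outcome.

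**Cost.** A few sentences in each document, some extra analysis work, and contacting a few participants for visits already planned. Including people who trained little may give a less favourable estimate.
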